### 8.2.2 Sample size estimate to assess if study drug is promising for further study

Considering the highly refractory nature of the subjects to be enrolled in this study and our lack of understanding of the kinetics of response to pembrolizumab in the post HCT setting, the investigators will be cautious about the potential underestimation of response of this novel agent. In addition, several, but not all patients are expected to receive standard chemotherapy at some point during their on-study therapy, thereby potentially confounding interpretation of the response rate to study drug. Therefore, the following criteria will be used to assess if the study drug is promising for further study:

(a) if  $\geq 4$  subjects demonstrate evidence of clinical benefit the drug will be considered promising. With 20 subjects we would be 90% confident that the true clinical benefit rate (CBR) lies between 7% and 40%. The CBR will be assessed on both day 35 and day 77 as determined by the proportion of subjects who receive pembrolizumab monotherapy who achieve either stable disease (SD) or ORR prior to the addition of standard chemotherapy

(b) the observation of any CRs seen in subjects not receiving standard chemotherapy will be considered promising.

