#### **5.1.2 Subject Inclusion Criteria**

In order to be eligible for participation in this trial, the subject must:

1. Acute Myeloid Leukemia (AML), Acute Lymphoblastic Leukemia (ALL) or Myelodysplastic Syndrome (MDS) in confirmed relapse based on bone marrow examination after allogeneic HCT. Biopsy confirmed myeloid sarcoma or extramedullary AML may also be considered.
2. Confirmation of 'measurable disease' by blast % will be defined as a marrow blast percentage of > 5% by morphologic assessment on bone marrow examination. This criterion does not apply to myeloid sarcoma, or extramedullary leukemia, which must also show measurable lesion by CT, MRI, PET/CT or photograph (i.e. Leukemia cutis). If marrow blasts of ≤ 5% blasts are enumerated the patient may be eligible only if there is clear (probable or definite) flow cytometric, cytogenetic or molecular aberrations (e.g. FLT3-ITD, NPM1, etc.) documenting relapse of the leukemia associated clone defined prior to HCT.
3. Patient may not have received definitive salvage chemotherapy for their post-transplant relapse within the past 21 days. Use of hydroxyurea is permitted.
4. Be willing and able to provide written informed consent/assent for the trial
5. Be ≥ 18 years of age on day of signing informed consent
6. Be willing to provide tissue from bone marrow biopsies
7. Have a performance status of 0, to 1 on the ECOG Performance Scale. For purposes of HCT, this will correspond to a Karnofsky Performance status of ≥ 80%

8. Demonstrate adequate organ function as defined in Table 1, all screening labs should be performed within 10 days of treatment initiation

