12. Has known or suspected active central nervous system (CNS) metastases and/or carcinomatous meningitis. Patients with suspected CNS disease should have lumbar puncture performed to exclude this possibility. Subjects with previously treated brain metastases may participate provided they are stable (without evidence of progression by imaging for at least four weeks prior to the first dose of trial treatment and any neurologic symptoms have returned to baseline), have no evidence of new or enlarging brain metastases, and are not using steroids for at least 7 days prior to trial treatment. This exception does not include carcinomatous meningitis which is excluded regardless of clinical stability.
13. Has active autoimmune disease that has required systemic treatment in the past 2 years (i.e. with use of disease modifying agents, corticosteroids or immunosuppressive drugs). Replacement therapy (eg., thyroxine, insulin, or physiologic corticosteroid replacement therapy for adrenal or pituitary insufficiency, etc.) is not considered a form of systemic treatment.

14. Has a history of (non-infectious) pneumonitis that required steroids, or current pneumonitis
15. Has a history or current evidence of any condition, therapy, or laboratory abnormality that might confound the results of the trial, interfere with the subject's participation for the full duration of the trial, or is not in the best interest of the subject to participate, in the opinion of the treating investigator.
16. Has known psychiatric or substance abuse disorders that would interfere with cooperation with the requirements of the trial
17. Is pregnant or breastfeeding, or expecting to conceive or father children within the projected duration of the trial, starting with the pre-screening or screening visit through 120 days after the last dose of trial treatment
18. Has received prior therapy with an anti-PD-1, anti-PD-L1, or anti-PD-L2 agent
19. Has a known history of Human Immunodeficiency Virus (HIV) (HIV 1/2 antibodies)
20. Has known active Hepatitis B (e.g., HBsAg reactive) or Hepatitis C (e.g., HCV RNA [qualitative] is detected)
21. Has received a live vaccine within 30 days of planned start of study therapy

*Note: Seasonal influenza vaccines for injection are generally inactivated flu vaccines and are allowed; however intranasal influenza vaccines (e.g., Flu-Mist®) are live attenuated vaccines, and are not allowed.*

*\*Note:*

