#### 5.2.1.2 Dose Modification (Escalation/Titration/Other)

After initiated study treatment, the use of chemotherapy prior to day 35 bone marrow biopsy (or two cycles of pembrolizumab) is discouraged.

- Systemic Chemotherapy may be instituted in the following scenarios:

- Evidence for progressive AML or MDS on day 35 bone marrow biopsy. Progression will be defined as a minimum of > 5% increase in the absolute marrow blasts from pre-treatment biopsy. For example, increase in bone marrow blast from 10% on pretreatment biopsy to 25% on day 35 marrow examination OR

- At the discretion of the treating physician for impending rapidly progressive relapse (e.g. rapid increase in peripheral blast % or hematologic instability. These situations should be discussed in consultation with the study PIs OR
- Alternatively, subjects with minimal progression may remain on monotherapy if deemed there may be potential for subsequent clinical response or deemed poor candidates for systemic chemotherapy. For example, a subject who is tolerating pembrolizumab at day 35 of treatment with increase in bone marrow blasts to 15% at day 35 from 9% at pre-treatment will be recorded as progression but may remain on monotherapy to complete four dose of induction (phase I) at investigator's discretion.

- The chemotherapy regimen will be at the discretion of the treating physician and may include hypomethylation therapy or cytotoxic chemotherapy including high dose ara-C (e.g. FLAG) and/or anthracycline-based regimens. Other investigational agents are not permitted or the subject will be removed from further pembrolizumab and placed into follow-up.

Adverse events (both non-serious and serious) associated with pembrolizumab exposure may represent an immunologic etiology. These adverse events may occur shortly after the first dose or several weeks after the last dose of treatment. Pembrolizumab must be withheld for drug-related toxicities and severe or life-threatening adverse events (AEs) as per Table 3 below. Pembrolizumab must also be permanently discontinued in patients who develop  $\geq$  Grade 3 acute GvHD requiring systemic corticosteroids. Pembrolizumab should be temporarily held if acute GVHD grade II occurs. Pembrolizumab may be re-initiated once acute GVHD improves to < grade II. See Section 5.4 for supportive care guidelines, including use of corticosteroids.

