#### **5.3.1 Acceptable Concomitant Medications**

Patients may receive hydroxyurea at the discretion of their treating hematology physician as a temporary bridge to chemotherapy. All treatments that the investigator considers necessary for a subject's welfare may be administered at the discretion of the investigator in keeping with the community standards of medical care. All concomitant medication will be recorded on the case report form (CRF) including all prescription, over-the-counter (OTC), herbal supplements, and IV medications and fluids. If changes occur during the trial period, documentation of drug dosage, frequency, route, and date may also be included on the CRF.

All concomitant medications received within 14 days before the first dose of trial treatment and 30 days after the last dose of trial treatment should be recorded. Concomitant medications administered after 30 days after the last dose of trial treatment should be recorded for SAEs and ECIs as defined in Section 7.2.

FLT-3 inhibitors and tyrosine kinase inhibitors which are resumed as part of usual care after HCT are permissible.

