#### **7.1.1.5.3 Subsequent Anti-Cancer Therapy Status**

The investigator or qualified designee will review all new anti-neoplastic therapy initiated after the last dose of trial treatment. Once new anti-cancer therapy has been initiated the subject will move into survival follow-up.

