## **8.0 STATISTICAL ANALYSIS PLAN**

### **8.1 Statistical Analysis Plan Summary**

The statistical plan for this feasibility study of pembrolizumab for relapse after HCT is primarily directed toward the primary objective of safety and feasibility after HCT. The trial will additionally estimate the proportion of patients responding to pembrolizumab monotherapy by overall response rate (ORR). The ORR (CR+PR) will also be estimated at day 35 and 77 for subjects receiving  $\geq$  one dose of single agent pembrolizumab. If progression is noted subjects may receive standard induction chemotherapy. Subjects who are administered standard induction chemotherapy prior to day 77 (for any reason) will be considered non-responders for ORR of pembrolizumab monotherapy. However, we will perform a planned subset analysis to determine the ORR at day 77 for subjects receiving pembrolizumab followed by systemic chemotherapy.

The incidence of grade 3-4 acute GvHD and significant ( $\geq$  grade 3) immune mediated toxicities will be estimated at the conclusion of the treatment period which is 30 days after the last dose of pembrolizumab. Overall survival (OS) and Disease Free Survival (DFS) at 12 months will be calculated by Kaplan Meier methods. The observation period for OS and DFS will begin at the confirmed date of relapse after HCT until death or last scheduled clinical follow up. These observations will assist in determining whether further investigations are warranted after HCT.

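### Rule (b) in 8.2.2 excludes only standard chemotherapy, so one CR on a permitted FLT-3 inhibitor or TKI could by itself make pembrolizumab promising; exposure is probably small and may be zero

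*Combined protocol and SAP*

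**What the plan says.** Section 8.2.2 gives two criteria for calling pembrolizumab promising for further study. Rule (a) needs at least 4 of 20 subjects with clinical benefit, defined as "either stable disease (SD) or ORR prior to the addition of standard chemotherapy". Rule (b) is that "the observation of any CRs seen in subjects not receiving standard chemotherapy will be considered promising".

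On other anti-leukemic drugs, section 5.3.1 states that "FLT-3 inhibitors and tyrosine kinase inhibitors which are resumed as part of usual care after HCT are permissible". It also permits hydroxyurea as a bridge, and it requires all concomitant medication to be recorded on the CRF. Section 5.3.2 does not list FLT-3 inhibitors or TKIs among the prohibited therapies. Section 5.2.1.2 says that on-protocol chemotherapy "may include hypomethylation therapy or cytotoxic chemotherapy including high dose ara-C (e.g. FLAG) and/or anthracycline-based regimens"; targeted inhibitors are not named.

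In section 8.1, subjects given standard induction chemotherapy before day 77 "will be considered non-responders for ORR of pembrolizumab monotherapy". There is no equivalent provision for a targeted agent. The CR definition in 8.2.2.1 sets no condition on concomitant treatment.

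**The concern.** The lead-in to 8.2.2 explains that chemotherapy may confound the response to study drug, and the criteria follow from that. Rule (b) is therefore meant to pick out CRs not explained by other anti-leukemic treatment. It controls for one such treatment and is silent on another that the protocol expressly allows. Because a single CR decides it, one misattributed response is enough.

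The situation can arise under the entry criteria. Section 5.1.2 lets subjects with low marrow blasts qualify on "cytogenetic or molecular aberrations (e.g. FLT3-ITD, NPM1, etc.) documenting relapse of the leukemia associated clone defined prior to HCT", and 8.2.2.1 then makes their CR depend on that aberration disappearing. A subject could clear an FLT3-ITD clone while taking a permitted FLT-3 inhibitor and be scored as a CR without chemotherapy. At stake is whether one of the two stated criteria for further study can be met by another drug's effect.

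**Working it through.** **The plan's own figure.** The only precision figure in 8.2.2 is a 90% interval of 7% to 40% for the clinical benefit rate (CBR). An exact (Clopper-Pearson) 90% interval for 4/20 is 7.1% to 40.1%, so it reproduces. No operating characteristic is given for rule (b).

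**Inputs.** From the documents: N = 20; rule (a) threshold 4; rule (b) threshold 1. Assumed, because the documents do not give them:
- k, the number of subjects who start or resume an FLT-3 inhibitor or TKI after relapse: 0, 1 or 2
- r, the CR rate from that agent alone: 0 to 20%
- p, the background CBR among subjects without an inhibitor CR: 10%, 20% or 30%
- pembrolizumab produces no CRs

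**Step 1: rule (b) met falsely.** The probability is 1 − (1 − r)^k.

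| r | k = 0 | k = 1 | k = 2 |
|---|---|---|---|
| 0 | 0 | 0 | 0 |
| 1% | 0 | 0.010 | 0.020 |
| 2% | 0 | 0.020 | 0.040 |
| 5% | 0 | 0.050 | 0.098 |
| 10% | 0 | 0.100 | 0.190 |
| 20% | 0 | 0.200 | 0.360 |

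**Step 2: rule (a) alone.** P(Bin(20, p) ≥ 4) = 0.133, 0.589 and 0.893 at p = 10%, 20% and 30%. Stable disease counts as benefit, so the higher values are plausible. When they hold, rule (a) usually delivers the promising label anyway.

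**Step 3: overall effect of closing the gap.**
- As written: W = 1 − (1 − r)^k × P(Bin(20, p) ≤ 3).
- With rule (b) restricted and inhibitor CRs still counted as benefit under rule (a): R = 1 − Σ_c P(Bin(k, r) = c) × P(Bin(20 − c, p) ≤ 3 − c).

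Example with k = 2, r = 20%, p = 10%:
- W = 1 − 0.64 × 0.867 = 0.445
- R = 1 − (0.64 × 0.867 + 0.32 × 0.705 + 0.04 × 0.450) = 0.201
- W − R = 0.244

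W − R for k = 2:

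| r | p = 10% | p = 20% | p = 30% |
|---|---|---|---|
| 0 | 0 | 0 | 0 |
| 1% | 0.014 | 0.005 | 0.001 |
| 2% | 0.028 | 0.009 | 0.002 |
| 5% | 0.068 | 0.023 | 0.004 |
| 10% | 0.132 | 0.044 | 0.009 |
| 20% | 0.244 | 0.080 | 0.015 |

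For k = 1 and p = 10% the difference runs from 0.007 (r = 1%) to 0.141 (r = 20%). For k = 0 it is zero throughout.

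**Step 4: sensitivity lost.** With n countable subjects and true pembrolizumab CR rate q, the chance of at least one qualifying CR is 1 − (1 − q)^n. Section 8.2.2 expects several subjects to receive chemotherapy, so n may be well below 20; 12 is an assumed illustration.

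| Countable subjects, before → after setting aside 2 | q = 5% | q = 10% |
|---|---|---|
| 20 → 18 | 0.64 → 0.60 | 0.88 → 0.85 |
| 12 → 10 | 0.46 → 0.40 | 0.72 → 0.65 |

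**The case against.** The best defence is that the affected subjects may not exist. Section 5.3.1 covers resumed agents, which reads naturally as post-transplant maintenance. Subjects on maintenance may well have relapsed despite the drug, so a later CR is less easily credited to it. An agent newly started on study is arguably new anti-cancer therapy, and 7.1.1.5.3 says "Once new anti-cancer therapy has been initiated the subject will move into survival follow-up". Exclusion 15 in 5.1.3 lets the investigator keep out a subject with "any condition, therapy, or laboratory abnormality that might confound the results of the trial". The stated target throughout is monotherapy, and 8.2.2 opens by warning against underestimating response, so a sensitive rule is deliberate. The chemotherapy list in 5.2.1.2 is illustrative. Hydroxyurea and immunosuppression taper (8.2.4) confound too.

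Much of this stands as a limit on size: zero exposure is credible. It does not close the gap. Monotherapy is made operational only as absence of chemotherapy, and rule (b) does not use the word. Exclusion 15 is discretionary, applies at entry, and sits beside an express permission in 5.3.1. Exclusion 2 still allows one prior line of relapse-directed treatment. Section 7.1.1.5.3 concerns therapy begun after the last trial dose, and 7.1.4.5.1 concerns therapy not defined by the protocol, whereas resumed agents are permitted.

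A reader might infer from the mention of FLT3-ITD that inhibitor use is expected in this cohort. The documents do not say so; it is named only as an example of a marker of relapse.

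**Conclusion.** The gap in wording is real. Taken together, 5.3.1 and 8.2.2(b) allow one CR on a permitted targeted agent to meet a stated criterion alone, and nothing in section 8 flags it.

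The size rests wholly on assumed k, r and CBR. Over k = 0 to 2 and r = 0 to 20% with an inert drug, the false trigger probability for rule (b) is 0 to 0.36. The effect on the overall promising label is 0 to 0.24 at a CBR of 10% and at most about 0.015 at 30%. It matters only if someone is exposed and the background CBR is low.

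A reader might infer that the trial is likely to call an inactive drug promising. The documents do not support that: they give no exposure count, the true count may be zero, the analysis is descriptive (8.2.1), safety and feasibility are the primary endpoint (8.2.3), and the label only informs further study. The point is worth considering, with medium confidence.

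**What to change.** Change the SAP wording only:

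1. In 8.2.2(b), state that a CR counts alone only if the subject received neither standard chemotherapy nor an FLT-3 inhibitor or TKI started or resumed after the post-HCT relapse and before the response assessment.
2. Count a CR in a subject who continued an agent already in use at relapse, but report it as a flagged, separate category.
3. In 8.1, report monotherapy ORR and CBR overall, with N unchanged, and by concurrent FLT-3 inhibitor or TKI use. Do not score these subjects as non-responders for rule (a).
4. List hydroxyurea use and immunosuppression taper beside each CR.

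Rule (a) and what is permitted clinically do not change. Concomitant drugs are already on the CRF; start dates relative to relapse must be usable for items 1 and 2.

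The cost is the sensitivity loss in Step 4: if 2 subjects are set aside, about 0.03 to 0.04 with all 20 countable and about 0.06 to 0.07 with 12. The change does not fully isolate pembrolizumab. It removes one confounder from one of the two rules, and the listing in item 4 only makes the others visible.

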#### 8.2.2.1 Definition of Response.

For the purposes of this study, complete remission (CR) will be defined as achieving a morphologic leukemia free state by achieving all of the following criteria: bone marrow myeloblasts  $< 5\%$  by morphologic assessment; AND absence of circulating blasts with phenotypic or morphologic features of leukemia (e.g. Auer rods) AND no evidence of extramedullary disease. For subjects with  $\leq 5\%$  blasts but possessing flow cytometric, cytogenetic or molecular aberration (Sec 5.1); CR will also require resolution (absence) of that aberration. Partial remission (PR) will be defined as a  $\geq 50\%$  reduction in bone marrow blast percentage to 5-25% or marrow blasts  $< 5\%$  with persistent Auer rods, flow cytometric or cytogenetic disease. PR is not possible response designation for individuals entering with  $\leq 5\%$  blasts. SD will be defined as  $\leq 5\%$  increase in blasts or decreased blast percentage in the bone marrow that does not meet the criteria for PR. Progression will be defined as  $>5\%$  increase in bone marrow blast percentage from prior bone marrow aspirate. NOTE Given these patients have relapsed after allogeneic HCT blood count recovery is not considered at criteria for response in this protocol.

8.2.3 Stopping rules for futility: Study subjects will receive pembrolizumab  $\pm$  the addition of standard chemotherapy, therefore stopping rules for futility are not indicated. The primary endpoint of this study is safety and feasibility.

8.2.4 Stopping rules for toxicity: Patients will be monitored closely for the development of immune-mediated toxicity that may be attributable to pembrolizumab. For the purposes of this trial, we will consider the development of acute GvHD as a distinct entity from the known immune-mediated toxicity profile associated with PD1 blockade, though there may be clinical overlap. The impact of PD1 blockade on the development of acute GvHD following allogeneic HCT has not been studied in human subjects. Therefore, a rational approach will focus on whether there is an **increase** in the rates and severity of

acute GvHD and other immune mediated toxicities over the expected baseline. The following assumptions will be used to assess potential toxicities associated with this trial:

- All subjects will be inherently at risk for the development of GvHD as this study is limited to patients who have relapsed post-HCT. Although screening will exclude patients with active GvHD requiring immunosuppression, subjects will remain at risk independent of whether they receive study drug. The expected incidence of clinically significant grade 2 to 4 acute GvHD (requiring therapy) without Pembrolizumab is estimated to be 40-50%.
- Patients who relapse (without GVHD present) may still be receiving standard immunosuppression post-HCT to reduce the risk of inciting GVHD. Immunosuppressive medications (IS) may be withdrawn or tapered per usual care. Because patients are at risk for the development of GVHD within several weeks after IS withdrawal tapering may occur during administration of pembrolizumab at a rate determined by the treating physician. Due to timing of IS withdrawal overlapping with the treatment period for pembrolizumab, potentially confounding its relationship to the study drug, an aggregate summary of toxicity will be used to determine whether PD1 blockade is potentially associated with an increase in the severity of acute GvHD.
- For the purposes of this study, toxicity will be deemed as excessive if 12 of 20 subjects (60%) develop severe acute GvHD ( $\geq$  grade 3-4) OR  $\geq$  grade 3 immune related adverse events that do not improve to grade 1 after systemic corticosteroid treatment for 14 days. This study specific stopping rule is intended to capture excessive rates of severe acute GvHD (grades 3-4) as an adverse safety signal. We have set this threshold because some degree of GvHD is an anticipated consequence of usual withdrawal of immune-suppression and chemotherapy which is a current treatment standard for relapse. Grade 2 GvHD is associated with less morbidity and mortality compared to grades 3-4 and may be a potential surrogate of a beneficial anti-leukemic response (GvL), thus grade 2 GvHD will be recorded but not included in the stopping definition. The occurrence of severe acute GvHD for this toxicity rule will be monitored during the induction treatment period until 30 days after the last induction treatment dose of pembrolizumab given for the induction phase (doses 1-4).
- We will also make interim assessments after 10 and 15 patients have been observed for 30 days after the last induction dose of pembrolizumab. Specifically, further accrual will be halted if we observe at least 6 of 10 or 9 of 15 patients developing severe acute GvHD. If the true rates of severe acute GvHD are 30%, 40%, 50% or 60%, the study has respective probabilities of 0.05, 0.18, 0.43, and 0.71 of stopping early.
- 

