### 2.2 Trial Diagram

\* standard induction chemotherapy may be administered during induction at investigators discretion if concern for rapid clinical progression of malignancy (see 5.2.1.2).

† Primary study endpoint (s) are ORR (PR+CR) at day 35 and day 77

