Correlative Studies: Blood Collection§, ¶		X	D14 (+5)	D35 (±5)	D56 (±5)		X	D168 (±7) D252 (±7)		X	D425 (±14)†	X
Correlative Studies: Buccal Swabs		X										
Chimerism Analysis (VNTR) (Peripheral Blood)**		X		X			X			X		X

\*Phase II Maintenance treatment: For subjects achieving CR / PR as determined by day 77 response post-induction without significant pembrolizumab related toxicity. Subjects without CR / PR at day 77, relapse / progression after day 77 or clinically significant toxicity during the treatment will be considered off treatment and will be placed into follow-up.

†Follow up: Toxicity assessments will be for 30 days after last dose of pembrolizumab. Longer follow-up for up to 90 days, if applicable, based on continuing SAE / AE that was observed in the treatment period or an events of clinical interest (ECI). Follow up for survival will be up to 90 days after pembrolizumab or D455 (±14) for subjects completing

maintenance and a research blood collection will be obtained. Subjects not initiating or completing maintenance will complete 30 day toxicity assessments and then be followed only for survival (through D365 after initiating pembrolizumab). Subjects in CR/PR not completing maintenance for toxicity may have additional research specimens collected per investigators discretion (see below note). ‡ Relapse denotes collection of unplanned / unscheduled bone marrow aspirate, biopsy and correlative studies at time of clinical suspicion of relapse (if CR) or progression of malignancy at any time during treatment and follow-up periods.

§Bone marrow morphology based on aspirate and/or core biopsy, flow cytometry and  $\pm$  cytogenetics will be performed on day 35 (+5) after dose #2, day 77 ( $\pm$ 7) after dose #4, day 365 ( $\pm$ 14) after completing maintenance. An end of treatment bone marrow may be performed prior to day 365 in subjects in CR/PR who do not complete full maintenance therapy due to toxicity. Subjects removed from further treatment due to documented relapse are not required to undergo further bone marrow studies for research purposes. Cytogenetic analysis may be omitted if there are not pre-treatment cytogenetic anomalies of clinical interest.

||Comprehensive Serum Chemistry Panel should include Magnesium and Phosphorus.

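### Section 8.2.2.1 scores a marrow cleared to below 5% with residual extramedullary disease as SD, but a lesser response with the same lesion as PR, so the ORR categories are not monotone

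*Combined protocol and SAP*

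**What the plan says.** Section 2.2 of the combined protocol and SAP states: "Primary study endpoint (s) are ORR (PR+CR) at day 35 and day 77". Section 4.2.2 also lists ORR among the primary efficacy endpoints. Response is defined in section 8.2.2.1:

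- **CR** needs marrow blasts below 5%, "absence of circulating blasts with phenotypic or morphologic features of leukemia (e.g. Auer rods"), "AND no evidence of extramedullary disease".
- **PR, limb 1** is a fall of at least half, worded as "reduction in bone marrow blast percentage to 5-25% or marrow blasts"; the last three words open limb 2. Limb 1 sets no condition on blood or extramedullary sites.
- **PR, limb 2** is marrow below 5% "with persistent Auer rods, flow cytometric or cytogenetic disease". Extramedullary disease is not on this list.
- PR is not available to a subject who enters with 5% blasts or fewer.
- **SD** includes a "decreased blast percentage in the bone marrow that does not meet the criteria for PR".

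Section 5.1.2 admits extramedullary disease: "Biopsy confirmed myeloid sarcoma or extramedullary AML may also be considered". It does not bar marrow disease at the same time. The footnote to the flow chart in section 6.0 places "Subjects without CR / PR at day 77" off treatment, and section 5.2 makes PR or CR at day 77 a condition for maintenance.

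**The concern.** A response scale should not give a subject a worse category for having less disease. Here the conditions that block CR and those that qualify for PR below 5% do not match: extramedullary disease blocks CR but does not qualify for PR. A subject who falls between the two drops to SD, past a category that a lesser response would have earned.

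Two things are at stake. First, ORR is CR plus PR, so a deep marrow response with a residual lesion is lost from a listed primary efficacy endpoint. Section 8.2.2 itself says the investigators are wary of underestimating response. Second, the same label is used at day 77 to decide who enters maintenance. In an open-label, single-center trial, a case-by-case reading would affect both the endpoint and later exposure.

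**Working it through.** **The plan's own figure.** Section 8.2.2 gives a 90% interval of 7% to 40% for CBR with 20 subjects, alongside the threshold of four. The exact (Clopper-Pearson) limits for x of n are the 5% quantile of Beta(x, n-x+1) and the 95% quantile of Beta(x+1, n-x). With x = 4 and n = 20 they are 7.1% and 40.1%, which reproduces the stated figure. The point made here disputes no number in the plan.

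**Literal scoring.** Take a subject who enters with 40% marrow blasts and an extramedullary lesion, with no circulating blasts at assessment.

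| Marrow at assessment | Auer rods, flow or cytogenetic disease | Lesion | Rule met | Score |
|---|---|---|---|---|
| 10% | either | present | Limb 1: (40-10)/40 = 75% fall, within 5-25% | PR |
| 3% | persistent | present | Limb 2 | PR |
| 3% | absent | present | CR fails on the lesion; limb 1 fails (below 5%); limb 2 fails (no listed feature) | SD |
| 3% | absent | absent | All CR conditions | CR |

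The third row has less disease than either of the first two and scores lower.

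**Which baselines are affected.**

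- *Within limb 2, every baseline above 5%.* At 8% to 3% with the lesion present, persistent flow disease gives PR and cleared flow disease gives SD.
- *Between limb 1 and limb 2, baseline of at least 10%.* Limb 1 needs a follow-up value of at least 5% and at most half of baseline, so baseline must be at least 2 x 5% = 10%. At 15%, a fall to 5% (66.7%) is PR, while 3% with the lesion alone is SD.
- *The specific comparison with 10% follow-up marrow* needs a baseline of at least 2 x 10% = 20%. At 15%, a fall to 10% is 33.3% and is SD.
- *Baseline of 5% or less.* PR is barred, so this inversion does not arise.

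**Effect on ORR.** Taking 20 subjects as the denominator, each affected subject moves ORR by 1/20 = 5 points. For example, 3/20 = 15% (90% exact interval 4.2% to 34.4%) would be 4/20 = 20% (7.1% to 40.1%) if one such subject were PR.

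**Effect on CBR.** CBR counts SD, PR and CR. Three responders plus one SD is 4/20; four responders and no SD is also 4/20. Neither CBR nor the threshold of four moves. The second criterion in section 8.2.2, any CR without chemotherapy, does not move either, because the subject is not a CR on either scoring.

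**The case against.** **Circulating blasts.** A reader might infer that they create an equal gap. The text does not support that. The blasts that block CR are those with leukemic phenotype or morphology, and limb 2 names Auer rods and flow cytometric disease without confining them to marrow. Such subjects will mostly be PR. The gap remains only for blasts called on morphology alone, without Auer rods, flow or cytogenetic findings, or if limb 2 is read as marrow findings only.

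**Narrowness.** The subject must clear marrow, flow and cytogenetics while a lesion persists. A subject with persistent flow or cytogenetic disease is already PR. This stands, and it limits the expected count. It does not confine the problem to baselines of 10% or more, because the comparison within limb 2 applies at every baseline above 5%.

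**Little decision weight.** ORR has no threshold, section 8.2.1 calls the analysis descriptive, section 8.2.3 names safety and feasibility as the primary endpoint, and the criteria for a promising drug are unaffected. All of this is correct. ORR is nevertheless listed as primary in sections 2.2 and 4.2.2 and will be reported as such.

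**SD may be the intended score.** A sponsor could hold that a residual lesion should preclude PR. That is a coherent position, but limb 1 does not apply it, and limb 2 does not apply it when flow disease persists. The inconsistency remains whichever label is preferred.

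**Conclusion.** The definition is wrong as written. For subjects entering with more than 5% marrow blasts whose only residual disease is extramedullary, section 8.2.2.1 assigns SD, while a lesser response with the same lesion is PR. No other section repairs this. The size is 5 percentage points of ORR per affected subject, assuming a denominator of 20 and that the subject would otherwise count as PR. CBR and both criteria for a promising drug are unaffected.

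A reader might want to attach a probability that at least one subject is affected. The documents give neither the frequency of combined marrow and extramedullary disease nor the rate of marrow clearance with a residual lesion, so any such figure would rest on unsupported assumptions. A reader might also infer that the study's conclusion on whether the drug is promising is biased, or that subjects are wrongly taken off treatment. The first does not follow, because SD counts as benefit. The second is a clinical question that the documents do not settle; they show only that one ambiguous label serves both scoring and maintenance.

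**What to change.** Amend section 8.2.2.1 so that, for ORR scoring, both PR limbs treat extramedullary disease the same way. In a subject who entered with more than 5% marrow blasts, marrow below 5% that fails CR only because of residual extramedullary disease (or circulating blasts) should not rank below 5-25% marrow, or below marrow under 5% with persistent flow disease, when the other residual disease is the same. This can be done by adding those reasons to the limb 2 list, or by placing the same extramedullary condition on both limbs. The sponsor should choose and state the choice before scoring.

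Any qualifier about lesion growth must apply to both limbs or to neither. If it sat on limb 2 only, a subject with an enlarging lesion would still be PR at 40% to 10% and SD at 40% to 3% with flow and cytogenetics negative.

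The cost is one sentence. Extramedullary status must already be judged for CR, so the basic change needs no new test. A growth qualifier would cost more: the efficacy measurements in section 6.0 schedule no serial imaging or photography, and the protocol defines no growth criterion. If PR is widened, the report should say that ORR includes marrow-clearing responses with residual extramedullary disease.

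Because section 5.2 and the section 6.0 footnote tie maintenance to the day-77 label, the sponsor must reconcile them with the revised definition. No treatment rule is proposed here.
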